14.5.2 Data from the ongoing study LGX818X2101

Table 14-16 Data from LGX818X2101- as of 23/Nov/2011

Dose of LGX818 (mg)	Nr. DLTs / Nr. evaluable patients
100 (micro-emulsion)	1/4

14.5.3 LGX818 change in regimen

If a different regimen (BID and/or every-other-day) for LGX818 is explored in this study, then two models will be fitted independently for the different dosing regimens. The dose escalation for the originally planned regimen will be guided by the model described on [Section 10.4.2.1](#). The dose escalation for the new regimen (NR) will be guided by a model using the same mathematical relationship as the one for the originally planned regimen but with different prior distributions based on a meta-analytic predictive approach.

The parameters in the model for the new regimen (NR) will be denoted by γ_1, δ_1 for the LGX818 NR, by γ_2, β_2 for MEK162 BID, and by η_{NR} for the interaction parameter. The respective total daily doses will be denoted by b_1 and b_2 , respectively. This model can thus be expressed as:

$$\text{logit}(\mu_1(b_1)) = \log(\gamma_1) + \delta_1 \log(b_1/b_1^*)$$

$$\text{logit}(\mu_2(b_2)) = \log(\gamma_2) + \delta_2 \log(b_2/b_2^*)$$

$$\text{Odds}(\mu_{12}(b_1, b_2)) = \mu_{12}(b_1, b_2) / (1 - \mu_{12}(b_1, b_2))$$

$$= \exp(\eta_{NR} b_1/b_1^* b_2/b_2^*) (\mu_1(b_1) + \mu_2(b_2) - \mu_1(b_1)\mu_2(b_2)) / ((1 - \mu_1(b_1))(1 - \mu_2(b_2))),$$

where $b_1^* = 100\text{mg}$ (NR) and $b_2^* = 60\text{mg}$ (BID).

14.5.3.1 Prior specifications for LGX818 new regimen

At the time when a NR is introduced, the prior distribution for the parameters $\gamma_1, \delta_1, \gamma_2, \delta_2$ and η_{NR} will be derived in the following way:

γ_1, δ_1 :

The posterior means, standard deviations and correlation of $\log(\alpha_1), \log(\beta_1)$ incorporating all the data available at the time when a NR is introduced will be found via simulation.

The assumption about heterogeneity will be captured in the prior distributions of the standard deviation of $(\log(\gamma_1), \log(\delta_1))$, denoted by τ_1 and τ_2 . Both τ_1 and τ_2 follow a log-normal distribution with mean $\log(0.2)$ and standard deviation 0.01, assuming small to moderate between-regimen heterogeneity.

The updated model parameter will be estimated via simulation from the predictive distribution. Means, standard deviations and correlation of this distribution will then be used as the prior distribution for the parameters $(\log(\gamma_1), \log(\delta_1))$.

γ_2, δ_2 :

since the parameters γ_2, δ_2 relate to the single-agent (the marginal) dose-toxicity relationship of MEK162, for which the same regimen will be used, no heterogeneity is expected. Therefore, the prior for γ_2, δ_2 will simply be the posterior means, standard deviations and correlation of $\log(\alpha_2), \log(\beta_2)$ incorporating all the data available at the time when a BID regimen is introduced, found via simulation.

η_{NR} :

the posterior mean and standard deviation of η , denoted by $\text{mean}(\eta|\text{data}), \text{sd}(\eta|\text{data})$, incorporating all the data available at the time when a NR is introduced will be found via simulation. Based on the assumption of small to moderate between-regimen heterogeneity, the prior distribution of η_{NR} can be found analytically, as a normal distribution with mean = $\text{mean}(\eta|\text{data})$ and standard deviation = $(\text{sd}(\eta|\text{data})^2 + 2*0.2^2)^{0.5}$.

14.5.4 Operating characteristics of the Bayesian Logistic Regression Model and hypothetical dose escalation scenarios

14.5.4.1 The Bayesian logistic regression model

An adaptive Bayesian logistic regression model (BLRM) guided by the escalation with overdose control (EWOC) principle will guide the dose escalation of the combination treatment to its MTD(s)/RP2D(s). The use of Bayesian response adaptive models for Phase I studies has been advocated by the EMEA guideline on small populations (2006) and by (Rogatko 2007) and is one of the key elements of the FDA's Critical Path Initiative.

A 5-parameter BLRM (refer to the protocol [Section 10.4.2](#) for detail) for combination treatment will be fitted on first 28 day dose limiting toxicity data (i.e. absence or presence of DLT) accumulated throughout the dose escalation to model the dose-toxicity relationship of LGX818 and MEK162 when given in combination. To check the performance of the model, the document summarizes the simulation results and some hypothetical dose escalation scenarios.

Details regarding dose recommendation are described in [Section 10.4.2](#) of the protocol.

14.5.5 Simulated operating characteristics

14.5.5.1 Hypothetical scenarios

In order to show how the Bayesian combination model reacts, the following hypothetical scenarios were investigated:

- Scenario 1: no increases in odds of DLT, i.e., the simulation parameter values for the BLRM are set to the mean values of the prior.
- Scenario 2: is scenario 1 + 50% increase in odds of DLT, i.e., 50% increase in odds of DLT.

- Scenario 3: is scenario 1 + 100% increase in odds of DLT, i.e., 100% increase in odds of DLT.
- Scenario 4: is scenario 1 but with constant interaction across doses.
- Scenario 5: is scenario 2 but with constant interaction across doses.

Scenarios 4 and 5 represent stress tests since the underlying interaction is assumed constant across doses and not dose-dependent (as assumed in the model).

Table 14-17 True underlying probabilities of DLT for Scenario 1

LGX818 -QD (mg)	MEK162 - BID (mg)			
	15	30	45	60
30	0.035	0.039	0.06	0.126
50	0.076	0.081	0.103	0.169
100	0.203	0.213	0.239	0.304
150	0.331	0.349	0.38	0.443
200	0.445	0.469	0.504	0.564
250	0.539	0.568	0.606	0.662
300	0.615	0.648	0.686	0.737
350	0.676	0.711	0.749	0.795
400	0.725	0.761	0.797	0.839
450	0.765	0.8	0.835	0.872

Bold values indicate dose combinations in the targeted toxicity interval [16%, 35%)

Table 14-18 True underlying probabilities of DLT for Scenario 2

LGX818 -QD (mg)	MEK162 - BID (mg)			
	15	30	45	60
30	0.036	0.041	0.066	0.141
50	0.08	0.089	0.118	0.2
100	0.22	0.249	0.298	0.396
150	0.366	0.421	0.491	0.594
200	0.495	0.57	0.651	0.744
250	0.601	0.686	0.767	0.844
300	0.684	0.772	0.845	0.904
350	0.748	0.833	0.896	0.941
400	0.798	0.877	0.93	0.963
450	0.837	0.909	0.952	0.977

Bold values indicate dose combinations in the targeted toxicity interval [16%, 35%)

Table 14-19 True underlying probabilities of DLT for Scenario 3

LGX818 -QD (mg)	MEK162 - BID (mg)			
	15	30	45	60
30	0.037	0.043	0.07	0.151
50	0.083	0.095	0.13	0.224
100	0.232	0.277	0.345	0.466
150	0.391	0.474	0.572	0.692
200	0.531	0.639	0.742	0.838
250	0.643	0.758	0.849	0.917
300	0.729	0.839	0.912	0.957
350	0.793	0.892	0.948	0.978
400	0.841	0.927	0.969	0.988
450	0.876	0.95	0.981	0.994

Bold values indicate dose combinations in the targeted toxicity interval [16%, 35%)

Table 14-20 True underlying probabilities of DLT for Scenario 4

LGX818- QD (mg)	MEK162 - BID (mg)			
	15	30	45	60
30	0.035	0.038	0.058	0.121
50	0.075	0.078	0.097	0.157
100	0.196	0.198	0.215	0.267
150	0.316	0.319	0.333	0.377
200	0.422	0.424	0.436	0.474
250	0.51	0.512	0.522	0.554
300	0.582	0.583	0.592	0.619
350	0.64	0.641	0.649	0.672
400	0.687	0.688	0.695	0.715
450	0.726	0.727	0.733	0.75

Bold values indicate dose combinations in the targeted toxicity interval [0.16, 0.35)

Table 14-21 True underlying probabilities of DLT for Scenario 5

LGX818 -QD (mg)	MEK162 - BID (mg)			
	15	30	45	60
30	0.051	0.056	0.084	0.171
50	0.108	0.113	0.139	0.218
100	0.267	0.271	0.291	0.353
150	0.41	0.412	0.428	0.476
200	0.523	0.525	0.537	0.574
250	0.61	0.611	0.621	0.651
300	0.676	0.677	0.685	0.709
350	0.727	0.728	0.735	0.755
400	0.767	0.768	0.774	0.79
450	0.799	0.8	0.804	0.819

Bold values indicate dose combinations in the targeted toxicity interval [0.16, 0.35)

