10.4.2 Statistical hypothesis, model, and method of analysis

10.4.2.1 Phase Ib

An adaptive BLRM guided by the EWOC principle will guide the dose escalation of the combination treatment to its MTD(s)/RP2D(s). A 5-parameter BLRM for combination treatment will be fitted on the dose-limiting toxicity data (i.e. absence or presence of DLT) accumulated throughout the dose escalation, for modeling the dose-DLT relationship of LGX818 (capsule formulation) and MEK162 when given in combination. While developing dual combination (LGX818 and MEK162) all information available about the dose-DLT relationship of the single agents LGX818 (i.e., from [LGX818X2101] study on both the capsule and micro-emulsion formulations) and MEK162 [ARRAY-162-111 study] will be summarized in prior distributions, based on a meta-analytical predictive approach to properly down-weight the information. The 5 parameter BLRM will be extended to a 10-parameter BLRM to model the dose-DLT relationship of LGX818 (capsule formulation) and MEK162 and LEE011 when given in combination. Three week on 1 week off DLT data from [CLEE011X2101] will be summarized in prior distributions based on a meta-analytical predictive approach to properly down-weight the information.

The 5-parameter BLRM for MEK162 original tablet

The 5-parameter BLRM is formulated in the following way: Let $\pi_1(d_1)$ be the probability of a DLT if LGX818 is given as a single agent at dose d_1 , and $\pi_2(d_2)$ the probability of a DLT if MEK162 is given as a single agent at dose d_2 . The dose-response relationship is then modeled as:

$$\text{LGX818: } \text{logit}(\pi_1(d_1)) = \log(\alpha_1) + \beta_1 \log(d_1/d_1^*)$$

$$\text{MEK162 original tablet: } \text{logit}(\pi_2(d_2)) = \log(\alpha_2) + \beta_2 \log(d_2/d_2^*)$$

$$\begin{aligned} \text{Odds}(\pi_{12}(d_1, d_2)) &= \pi_{12}(d_1, d_2) / (1 - \pi_{12}(d_1, d_2)) \\ &= \exp(\eta_{12}(d_1/d_1^*)(d_2/d_2^*)) (\pi_1(d_1) + \pi_2(d_2) - \pi_1(d_1)\pi_2(d_2)) / ((1 - \pi_1(d_1))(1 - \pi_2(d_2))), \end{aligned}$$

where

- $\text{logit}(\pi(d)) = \log[\pi(d) / \{1 - \pi(d)\}]$, $\pi(d)$ is the probability of a DLT at dose d ,
- $\pi_{12}(d_1, d_2)$ is the probability of a DLT given the combination doses
- $d_1^* = 100\text{mg}$ and $d_2^* = 60\text{mg}$ are the reference doses of LGX818 and MEK162 original tablet respectively,

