10.8 Sample size calculation

Phase Ib

Dose escalation: Cohorts of 3 to 6 evaluable patients will be enrolled in the dose escalation part including at least six patients at the MTD/RP2D level, as described in [Section 6.2.4](#).

Multiple cohorts may be sequentially enrolled to the same dose level. Additional cohorts of 1 to 6 patients may be enrolled at any dose level below the estimated MTD/RP2D for further elaboration of safety and PK parameters as required. At least 18 patients are expected to be treated in the dual-combination dose-escalation part of the study, for the model to have reasonable operating characteristics relating to its MTD recommendation (see [Appendix 5](#) for details). At least 12 patients are expected to be treated in the triple-combination dose-escalation part of the study.

Phase II

Arm 1 dual combination: Based on the prior distribution and decision rules described in [Section 10.4](#), it was explored how likely it is to wrongly declare activity given the true DCR = 20%, and how likely it is to correctly declare activity given the true DCR = 40%, when 28 patients are evaluated.

- If the true DCR = 20%, the probability to wrongly declare activity (i.e. seeing at least 9 patients with SD or better) is 9.0%.
- If the true DCR = 40%, the probability to correctly declare activity (i.e. seeing at least 9 patients with SD or better) is 85.2%.

If 9 out of 28 patients have at least SD or better, then the posterior risk of the true DCR being in the unacceptable category is 7.0%.

Note: if the interim analysis is performed, the probability to correctly declare activity if the true DCR = 40% is 82.3%.

Arm 2 dual combination: Based on the prior distribution and decision rules described in [Section 10.4](#), it was explored how likely it is to wrongly declare activity given the true ORR = 10%, and how likely it is to correctly declare activity given the true ORR = 20%, when 41 patients are evaluated:

- If the true ORR = 10%, the probability to wrongly declare activity (i.e. seeing at least 7 responses) is 11.0%.
- If the true ORR = 20%, the probability to correctly declare activity (i.e. seeing at least 7 responses) is 73.9%.

If 7 out of 41 patients have PR or CR, then the posterior risk of the true ORR being in the unacceptable category is 9.8%.

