A weakly informative prior reflecting the current uncertainty about the toxicity of the combination treatment is used for η_{12} . In order to allow for the potentiality of both synergy and antagonism of the safety profiles, it was assumed that η_{12} is normally distributed with median

= 0 (no increase on odds of DLT, i.e. independence) and 97.5th percentile = $\log(20)$ (20-fold increase on odds of DLT).

The prior distributions of 5 parameter dual combo (LGX818+MEK162) model are provided in [Table 14-14](#).

Table 14-14 Predictive distribution of model parameters

Parameter	Means	Standard deviations	Correlation
$\log(\alpha_1), \log(\beta_1)$	-1.415, 0.463	1.231, 1.273	0.003
$\log(\alpha_2), \log(\beta_2)$	-2.326, 1.564	1.107, 1.368	-0.535
η_{12}	0	1.528	N/A

For LGX818X2101, data up to dose escalation teleconference from 23/Nov/2011

Predictive: between-trial heterogeneity $\tau_1 \sim \text{lognormal}(\log(0.25), 0.01^2)$, $\tau_2 \sim \text{lognormal}(\log(0.25), 0.01^2)$ for $\log(\alpha_1)$, $\log(\beta_1)$, and $\tau_1 \sim \text{lognormal}(\log(0.25), 0.01^2)$, $\tau_2 \sim \text{lognormal}(\log(0.25), 0.01^2)$ for $\log(\alpha_2)$, $\log(\beta_2)$

A summary of the respective prior distribution of DLT rates for dual combo (LGX818+MEK162) is given in [Table 14-15](#). Dose combinations not satisfying the overdose criteria, i.e. not eligible at the start of the study, are displayed in bold.

Note: the model was re-evaluated before the first dose escalation meeting with the available data from study [[CLGX818X2101](#)].

Table 14-15 Summary of prior probabilities of DLT rates

LGX818 (mg)	Prior probabilities that Pr(DLT) is in interval:			Mean	SD	Quantiles		
	[0.0, 0.16)	[0.16, 0.35)	[0.35, 1.00]			2.50%	50.00%	97.50%
MEK162 = 30mg								
50	0.674	0.206	0.12	0.147	0.166	0	0.086	0.616
100	0.379	0.29	0.331	0.288	0.226	0.018	0.226	0.824
150	0.231	0.199	0.571	0.472	0.32	0.021	0.433	0.999
200	0.203	0.152	0.644	0.551	0.347	0.017	0.573	1
250	0.198	0.124	0.679	0.595	0.361	0.011	0.677	1
300	0.198	0.105	0.697	0.621	0.37	0.007	0.754	1
MEK162 = 45mg								
50	0.615	0.231	0.154	0.173	0.18	0.001	0.109	0.668
100	0.365	0.254	0.381	0.319	0.256	0.014	0.249	0.891
150	0.255	0.165	0.58	0.489	0.342	0.011	0.466	0.999
200	0.238	0.123	0.639	0.559	0.37	0.006	0.616	1
250	0.238	0.098	0.664	0.596	0.385	0.003	0.722	1
300	0.242	0.083	0.675	0.616	0.395	0.001	0.798	1
MEK162 = 60mg								
50	0.453	0.297	0.25	0.242	0.202	0.016	0.182	0.754

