14.5.5.4 Results

Table 14-23 presents the model for the 5 different scenarios studied, additionally showing how many of the trials were stopped before declaring MTD when all dose combinations were considered too toxic.

Table 14- Results

Scenario	Metric						
	I	II	III	IV	V	VI	Stopped
1	0.681	0.035	0.286	0.882	0.016	0.076	0.026
2	0.532	0.147	0.32	0.716	0.126	0.122	0.036
3	0.552	0.099	0.35	0.78	0.046	0.136	0.038
4	0.474	0.155	0.273	0.496	0.382	0.088	0.034
5	0.613	0.133	0.252	0.736	0.152	0.058	0.054

In summary, the simulated operating characteristics show:

- (Metric IV) that the identified MTD falls within the targeted interval in more than 72% of the cases, except for scenario 4.
- (Metric V) that on average, less than 15% of patients are treated at overly toxic doses, excluding scenario 4.
- (Metric I) The average proportion of patients receiving a target dose combination on study is 47% to 68%.
- Scenario 4 needs careful consideration, since the true underlying probability of DLT (15.7%) for the combination MEK162 60mg + LGX818 50mg is very close to the lower boundary of the targeted toxicity [16%, 35%). Unsurprisingly, this combination is therefore identified relatively often as an MTD. Had this combination been counted as a correct MTD as well, then metric IV improves to 56.8%.

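### Appendix 5 mislabels its simulation scenarios: the no-increase base case carries an interaction, and Scenario 4, excepted from two summary statements, is the real no-interaction case

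*Protocol*

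**What the plan says.** Section 10.8 sets the Phase Ib minimum for the dual combination: "At least 18 patients are expected to be treated in the dual-combination dose-escalation part of the study". The purpose it gives for this number, with a reference to Appendix 5 for the details, is "for the model to have reasonable operating characteristics relating to its MTD recommendation".

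Section 14.5.5.1 lists five true dose-toxicity scenarios. The first is described as "Scenario 1: no increases in odds of DLT, i.e., the simulation parameter values for the BLRM are set to the mean values", where the means meant are those of the prior distribution. Scenarios 2 and 3 are Scenario 1 with the odds of DLT raised by 50% and 100%. Scenarios 4 and 5 are Scenarios 1 and 2 with an interaction that is constant across doses, and both are called stress tests. Tables 14-17 to 14-21 print the true DLT probabilities for Scenarios 1 to 5.

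Section 14.5.1 gives the prior behind Scenario 1. The interaction is centred on "0 (no increase on odds of DLT, i.e. independence"), and Table 14-14 lists its mean as 0. In Section 10.4.2.1, 100 mg and 60 mg "are the reference doses of LGX818 and MEK162 original tablet respectively".

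The summary in Section 14.5.5.4 states "that the identified MTD falls within the targeted interval in more than 72% of the cases, except for scenario 4" and, under the tag Metric V, that on average "less than 15% of patients are treated at overly toxic doses, excluding scenario 4".

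**The concern.** A contradiction shows before any calculation. If Scenario 1 sits at the prior means, its interaction is 0, and there is nothing to hold constant across doses. Scenario 4, defined as Scenario 1 with constant interaction, would then have the same truth as Scenario 1. The two tables differ: 0.304 against 0.267 at 100/60 mg, and 0.872 against 0.750 at 450/60 mg. At least one label is wrong.

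It matters which one. The two scenarios have very different printed performance in Table 14-23, and the one with the poor figures is excepted from the statements on correct MTD selection and overly toxic doses. A reader of Section 10.8 takes the favourable row as the base case.

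**Working it through.** **Inputs.** Table 14-14 means: log(α1) = −1.415, log(β1) = 0.463, log(α2) = −2.326, log(β2) = 1.564, η12 = 0. Reference doses are 100 mg LGX818 and 60 mg MEK162 (Section 10.4.2.1). Dose pairs below are LGX818/MEK162 in mg.

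**Model (Section 10.4.2.1), written in odds.** o1 = exp(−1.415)·(d1/100)^1.589 and o2 = exp(−2.326)·(d2/60)^4.778, where exp(0.463) = 1.589 and exp(1.564) = 4.778. The combination odds are exp[η12·(d1/100)·(d2/60)]·[(1 + o1)(1 + o2) − 1].

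**Worked cell, 100/60.** o1 = 0.2429 and o2 = 0.0977, so with η12 = 0 the odds are 1.2429 × 1.0977 − 1 = 0.3643 and the probability is 0.3643/1.3643 = 0.267. That is the Scenario 4 entry. Multiplying the odds by 1.2 gives 0.4372/1.4372 = 0.304, the Scenario 1 entry.

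| Dose pair | η12 = 0 | Table 14-20 (Scenario 4) | η12 = log(1.2) | Table 14-17 (Scenario 1) |
|---|---|---|---|---|
| 100/60 | 0.267 | 0.267 | 0.304 | 0.304 |
| 150/45 | 0.333 | 0.333 | 0.380 | 0.380 |
| 450/60 | 0.750 | 0.750 | 0.872 | 0.872 |

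**All 40 cells of each table:**
- Table 14-20 (Scenario 4) is reproduced with no interaction (largest difference 0.0005). A constant multiplier of 1.2 misses it by up to 0.046.
- Table 14-17 (Scenario 1) is missed by up to 0.124 with no interaction. It is reproduced by a dose-dependent 1.2 (0.0006).
- Table 14-18 (Scenario 2) is reproduced by a dose-dependent 1.8 = 1.2 × 1.5 (0.0006), and Table 14-19 (Scenario 3) by 2.4 = 1.2 × 2.0 (0.0005).
- Table 14-21 (Scenario 5) is reproduced by a constant 1.5 on the no-interaction base (0.0005). It is not Scenario 2, at 1.8, with its interaction held constant.

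**Size of the hidden interaction in Scenario 1.** It scales with the product of the dose ratios: 1.2^0.075 = 1.01 at 30/15, 1.2 at 100/60, and 1.2^4.5 = 2.27 at 450/60. It moves combinations across the category limits. The pair 150/45 is excessive in Table 14-17 (0.380) but in target without interaction (0.333). The pair 50/60 is in target in Table 14-17 (0.169) but under-dosing without interaction (0.157).

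**Table 14-23 as printed:**

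| Scenario | I + II + III | II | IV | V | VI |
|---|---|---|---|---|---|
| 1 | 1.002 | 0.035 | 0.882 | 0.016 | 0.076 |
| 2 | 0.999 | 0.147 | 0.716 | 0.126 | 0.122 |
| 3 | 1.001 | 0.099 | 0.780 | 0.046 | 0.136 |
| 4 | 0.902 | 0.155 | 0.496 | 0.382 | 0.088 |
| 5 | 0.998 | 0.133 | 0.736 | 0.152 | 0.058 |

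The protocol explains Scenario 4 by the 50/60 combination, whose true rate of 15.7% is just below target. By its own figure, counting that combination as correct raises metric IV from 49.6% to 56.8%, a gain of 7.2 points. Those points come from metric VI. None of the 38.2% in metric V is explained.

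**Smaller slips.** Scenario 2 has 71.6%, which is not more than 72%. The bullet tagged Metric V speaks of patients treated, which is metric II. Metric V is the probability of recommending a toxic combination, and it is 15.2% in Scenario 5.

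**The case against.** A fair defence has several parts.

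- **Scenarios 2 and 3 are right relative to Scenario 1 as simulated.** At 100/60 the printed odds ratios are (0.396/0.604)/(0.304/0.696) = 1.50 and (0.466/0.534)/(0.304/0.696) = 2.00. This stands. A reader might infer that the 50% and 100% increases are false, but they fail only if measured from no interaction.
- **Scenario 4 is not hidden.** It has its own row, sets the lower end of the metric I range, and has a bullet asking for careful consideration. This stands. It is left out of two statements only, though that bullet is silent on the 38.2%.
- **The sentence on patients treated is true.** Metric II outside Scenario 4 is 3.5%, 14.7%, 9.9% and 13.3%, all below 15%. Only the tag is wrong. The 72% slip is 0.4 points.
- **Little now depends on the table.** Eighteen is a minimum, and simulated trials could reach 60 patients (Section 14.5.5.2). The model was re-evaluated before the first dose-escalation meeting (Section 14.5.1), and Table 14-27 already carries different LGX818 means. Both dual-combination RP2Ds are declared (Section 6.2.2) and enrolment is closed (Section 14.10.1). Escalation decisions also required clinical review. This limits the consequence to the recorded justification of the design, but does not make the labels correct.

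**Conclusion.** The labels are wrong as written. The case described as having no increase in odds carries a dose-dependent log(1.2) interaction, and the case described as a stress test is the prior-mean, no-interaction base. This rests only on the protocol's formula, its Table 14-14 means and its printed tables, and it holds in every cell.

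A reader might go further and infer that the design recommends an overly toxic MTD in 38.2% of trials under its own base case. The documents do not support that, because the Scenario 4 row cannot be trusted as printed. Its metrics I to III leave 9.8% of patients unaccounted for. Every true rate in Table 14-20 is also equal to or lower than its counterpart in Table 14-17, yet the printed chance of a toxic recommendation is 38.2% against 1.6%. Neither fact proves an error in metrics IV and V, but the row has to be verified before anyone relies on it. The escalation simulations are not reproduced here, so Table 14-23 is taken as printed.

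What follows is narrower. The protocol has no reliable, correctly labelled result for its no-interaction case, and the summary cited by Section 10.8 leaves that case out of its statements on correct selection and overly toxic doses.

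**What to change.** Choose one of two routes for the scenarios:

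1. Relabel them to match what was simulated: dose-dependent interaction of 1.2, 1.8 and 2.4 for Scenarios 1 to 3, no interaction for Scenario 4, and a constant 1.5 for Scenario 5.
2. Re-run with a distinct set of truths that includes η12 = 0. Re-running the list exactly as now described would not do, since Scenarios 1 and 4 would then be the same case.

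On either route:
- verify or re-run the Scenario 4 row of Table 14-23;
- present the η12 = 0 case as the base case and drop the stress-test label from it;
- correct the metric tag on the patients-treated bullet and the 72% figure;
- restate metrics II, IV and V across all scenarios, so that the reference in Section 10.8 rests on accurate figures.

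The cost is a re-run of existing code and a correction to the appendix. The stated performance may become less favourable.
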